7.1 Patient inclusion criteria

- Adult patients (≥ 18 years of age)
- Undergoing a surgical, radiological or cardiological procedure (interventional or diagnostic) with the primary method of anaesthesia planned to be general anaesthesia

7.2 Patient exclusion criteria

- Paediatric patients (< 18 years of age)
- Patients where the induction of general anaesthesia occurs in the emergency department (ED), critical care unit or general ward
- Patients in cardiac arrest at the time of airway intervention
- Patients having obstetric procedures (pregnant patients undergoing non-obstetric surgery will be included)

- Procedures planned to be performed under regional anaesthesia, local anaesthesia or sedation
- First set of observations outside the 96-hour study period
- Patients already with an airway device in place (e.g. ventilated patients transferred from ITU, tracheostomy)

8 Project procedures

8.1 Patient inclusion

Patients will be identified as eligible by local investigators using methods specific to the centre, however this will likely involve published operating lists and emergency theatre bookings. All eligible patients will be included if possible.

9 Data

9.1 Data to be collected

Data will be collected on all operating lists with patients who meet inclusion criteria in participating hospitals. Each hospital taking part will have nominated staff who will be responsible for data collection.

For each day of the study the local investigating team will determine the total number of patients eligible for inclusion.

For each included patient, the anaesthetist or anaesthetic assistant (e.g. operating department practitioner, anaesthetic nurse) will be asked to complete a paper case record form (CRF; *Appendix* 2). Where more than one anaesthetist is involved, the most senior anaesthetist should be asked to complete the CRF.

Completed CRFs will be collected from the treating anaesthetic team. Local investigators will be responsible for ensuring accuracy and completeness of data. Where appropriate, this should include cross-checking with patient notes and other sources of information.

Completed CRFs will be stored in a secure location accessible by the local PI and other named members of the study team in accordance with NHS Information Governance standards. Information from each paper CRF, as well as the total number of eligible patients for each day of the project, will be entered via a secure web-based portal onto a secure database. The database will have data validation rules built-in to ensure accurate data entry (e.g. range checks, and field validation).

No patient-identifiable information will be uploaded to the secure database. Each site may elect to use a local ID upon the CRF to facilitate retrospective data capture within the immediate time frame of the project however this should be detached once the CRF is completed and will not form part of the dataset uploaded to the data capture server. Paper CRFs will be retained by the local study team in a locked, secure location in the hospital for a period of 6 months after the project ends to allow queries about study quality to be addressed during data cleaning and analysis. The local ID will not remain upon the CRF during this period.

Additionally, the lead for each site will submit, via the on-line REDCap system, the study week that site has selected (from one of weeks commencing 1st, 8th, 15th, 22nd or 29th November), the total number of eligible procedures for each 24 hour period of the study, and the list of all local investigators involved in the study (to enable production of certificates to demonstrate involvement as well as to allow naming of all collaborators on any manuscripts arising from the study). The site details data capture form is provided in *Appendix 3*.

All investigators and any other individuals contributing to the study will be required to comply with the Data Protection Act 2018 and the NHS code of confidentiality.

Data to be collected:

- Site (automatically populated dependent upon the login credentials of the local investigator)
- Day of the study
- Age of patient (grouped into 18-39, 40-59, 60-79 and \geq 80 years)
- Sex of patient
- American Society of Anesthesiologists (ASA) physical status
- Patient body mass index (BMI), grouped into underweight (< 18.5 kg/m²), normal (18.5 24.9 kg/m²), overweight (25.0 29.9 kg/m²), class 1 obesity (30.0 34.9 kg/m²), class 2 obesity (35.0 39.9 kg/m²), class 3 obesity (>= 40.0 kg/m²)
- Surgical urgency (elective; expedited; urgent; emergency)
- Start time of procedure (first set of observations entered into the anaesthetic record), grouped into daytime (07:30–17:59); evening (18:00–23:59); and overnight (00:00–07:29)
- Surgical specialty
- Surgical severity (minor; intermediate; major)
- Location of procedure: within or outside the main operating theatre complex (including stand-alone day surgery units), used to identify "remote-site anaesthesia".
- Grade of anaesthetist managing airway (initial airway manager and second airway manager if required)
- PPE worn by anaesthetist managing airway:
 - Eye protection: visor; goggles; other

- Respiratory protection: surgical mask; disposable FFP2/3 mask; re-usable FFP2/3 mask; powered air-purifying respirator; other

- Body protection: plastic apron; long-sleeved gown; hazmat suit; other
- Gloves: single pair; double pair; other
- Airway management technique- pre-oxygenation, mask ventilation, apnoeic oxygenation
- Airway equipment utilised to maintain oxygenation and facilitate anaesthesia, divided into:
 - Airway devices utilised: facemask, supraglottic airway device; tracheal tube; other (including rigid bronchoscope, jet ventilator and transnasal humidified rapid-insufflation ventilatory exchange)
 - Airway techniques including: direct laryngoscopy; videolaryngoscopy; use of a flexible bronchoscope over which a tracheal tube is passed, categorised into whether performed awake or asleep
 - Use of cricoid force?

- Adjunct equipment including: bougie; stylet; Oxford or HELP pillow; high and lowflow nasal cannulae; aerosol boxes or drapes; as well as a free text option for other potential equipment

- Patient COVID-19 status:
 - Positive: RT-PCR or lateral flow test positive for SARS-CoV-2; OR symptoms consistent with COVID-19 with no SARS-CoV-2 test available; OR recent exposure to SARS-CoV-2
 - Negative: RT-PCR or lateral flow test negative for SARS-CoV-2 infection; AND actively cohorted with other COVID-19 negative patients for the entirety of their hospital stay prior to this operation; AND self-isolated according to institutional guidelines.
 - Unclear: No SARS-CoV-2 result available with no risk factors; OR not self-isolated according to institutional guidelines; OR not in a COVID-19-free pathway.
- Whether anaesthesia was terminated at the end of the procedure with a plan to wake up the patient (emergence from anaesthesia).

Airway complications:

- Number of tracheal intubation attempts.
 An attempt is defined by the number of times the laryngoscopy device is inserted or reinserted into the patient's airway.
- Best grade of laryngoscopy: modified Cormack and Lehane grading [9] into 1, 2a, 2b, 3 and 4.
- The following complications categorised into induction and emergence (defined as the period around the time of cessation of anaesthesia until hand over of patient to recovery/intensive care staff):
 - Airway trauma: evidence of airway bleeding or oedema.
 - Dental injury (arising solely from anaesthetic, rather than surgical, interventions)
 - Lip and mucosal injuries (arising solely from anaesthetic, rather than surgical, interventions)
 - Pulmonary aspiration: inhalation of oropharyngeal or gastric contents into the larynx and lower respiratory tract [10]
 - Change of intubation device: use of an additional airway device, e.g. change from supraglottic airway to tracheal tube, change from direct to videolaryngoscopy (or vice versa), use of bougie if not initially anticipated, change in type of laryngoscope e.g. McCoy vs Macintosh blade
 - Desaturation: reduction in oxygen saturations to ≤90% during airway management
 - Severe Desaturation: reduction in oxygen saturations to ≤80% during airway management
 - Difficult mask ventilation: need for two-person (or more) mask ventilation
 - Difficult SAD insertion: multiple insertion attempts; excessive leak; insufficient ventilation; change of SAD size/design

- Failed tracheal intubation even after intervention of a second airway manager, including:

- If oxygenation and provision of anaesthesia was possible via SAD and a decision was made to continue with surgery

- If a decision was made to wake the patient and abandon surgery
- If this resulted in death this should be recorded separately, as above
- Laryngospasm: unwanted muscular response of the larynx that produces partial or complete obstruction of the laryngeal airway [11].
- Oesophageal intubation (recognised): tracheal tube placed in the oesophagus and recognised before delivery of the fourth ventilatory breath
- Oesophageal intubation (delayed recognition): tracheal tube placed in the oesophagus and 4 or more ventilatory breaths delivered.
- Reintubation within 30 minutes of the end of the procedure
- Second airway manager: initial airway manager either requests the assistance of a second individual to directly manage the airway or the supervising anaesthetist requests a second individual to take over management of the airway.
- Emergency front-of-neck airway
- Death due to hypoxia or other complication of airway management.
- Significant deviation from original airway plan
- Subjective assessment of ease of 1) mask ventilation, 2) SAD placement and use, and
 3) tracheal intubation, using a 5-point Likert scale (1-5) with addition of "not attempted" for each question

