6.1 Study Design

AeroComp is service evaluation exploring the incidence of airway complications amongst patients undergoing general anaesthesia for surgical procedures within NHS Trusts. All adult patients undergoing any surgical procedure (with the exception of obstetric procedures) with the primary method of anaesthesia planned to be general anaesthesia will be eligible for enrolment to this study. The study duration will encompass 5 days (patients being enrolled over a 96 hour consecutive window with a further day of follow-up data collection) with an estimated total of 3600 patients being included. Individual sites are free to choose their own data collection window between 1st November

2021 and 3rd December 2021 as long as the 96 hour window commences at 07:30 on a Monday and closes at 07:29 on a Friday.

Primary outcome:

 Incidence of airway complications at both induction and emergence, defined as a composite of: airway trauma, aspiration, dental/lip/mucosal injury, change of intubation device, desaturation, three or more laryngoscopy attempts, grade 3 or 4 laryngoscopy, difficult face mask ventilation, difficult supraglottic airway device (SAD) usage, emergency front-of-neck airway, failed tracheal intubation, laryngospasm, oesophageal intubation (immediate or delayed recognition), requirement of reintubation immediately after extubation, and need for second intubator.

Secondary outcomes:

- Risk of composite outcome of airway complications will be reported for each individual component of the aerosol precaution bundle.
- Individual complications that comprise the primary outcome.
- Subjective operator assessment of airway difficulty
- Unanticipated airway difficulties necessitating significant deviation from the original airway plan.
- Composite risk of airway complication and association with confirmed/suspected COVID-19 infection, known negative COVID-19 infection without any potential COVID-19 risks, and all other patients.

7 List selection

Operating lists from all participating NHS hospitals will be included, with patients from those lists being eligible. Both elective and emergency cases will be included. The centres and local investigators will be identified by the Pan-London Perioperative Audit and Research Network (PLAN) or other national trainee research networks.

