9.2 Data handling and record keeping

All investigators and study staff will be required to comply with the requirements of the Data Protection Act 2018 with regard to the collection, storage, processing and disclosure of personal information and will uphold the Act's core principles.

Data will be collected onto paper CRFs by either local investigators or the anaesthetic team involved with the case. If local IT capabilities permit, data may be directly uploaded to the data capture service. Local investigators will also upload the total number of eligible patients for each 24 hour period of the study to identify capture rate.

Data will be uploaded by local investigators to the PLAN secure data capture server (https://www.planasm.org/redcap) which is hosted in a secure Tier 2 data centre in London Docklands with regular backup. The interface will use the REDCap v10.4.1 electronic CRF software. A REDCap ID for each patient included will be provided by the system for each new e-CRF uploaded. No uploaded data will contain patient-identifiable information.

All collected data will be anonymised. The following steps have been undertaken to ensure that patients cannot be reidentified from the collected data:

1) All ages are collected in bands.

2) No specific operation/procedure name is collected.

3) The date of surgery is not specifically collected, purely the day of the week upon which it took place in any one of five weeks within the data collection period.

4) No name, hospital number or NHS number is uploaded to the data collection server.

5) All sites are required to register the service evaluation with local Clinical Governance departments prior to recruitment to ensure any local issues are handled appropriately.

6) Caldicott Guardian approval at the lead site has been obtained (available to sites upon request)7) Information Governance approval at the lead site has been obtained (available to sites upon request).

10 Statistical considerations

10.1 Sample size calculation (some pilot/feasibility studies may not require a formal sample size calculation)

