Shaw *et al.* [12] reported an incidence of 91 airway complications in 1874 patients (~5%). Therefore, assuming an anticipated 5% incidence of our primary outcome in our study population, a desired error of +/-1% (absolute error) of our estimate for the incidence, and a 95% confidence level of achieving the desired estimate precision, we calculate the sample size required for our study to be \geq 1822 patients (Appendix 4; [13]). For a conservative estimate, with 50 centres each performing 18 procedures a day, we expect 3600 patients to be included, allowing acceptable rates of detection of rare events.

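### Airway difficulty is defined as the operator's rating, but the form goes to the most senior anaesthetist or an assistant, and the rater is not recorded

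*Protocol*

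**What the plan says.** Among the secondary outcomes in Section 6.1 of the protocol is "Subjective operator assessment of airway difficulty". The outcome is defined by who makes the judgement.

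Section 9.1 describes the item itself as "Subjective assessment of ease of 1) mask ventilation, 2) SAD placement and use, and" a third item on tracheal intubation, each scored 1 to 5 or marked as not attempted. It does not say who gives the score.

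Who completes the form is set in three places:

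- Section 9.1, general rule: "the anaesthetist or anaesthetic assistant (e.g. operating department practitioner, anaesthetic nurse) will be asked to complete a paper case record form".
- Section 9.1, where several anaesthetists are present: "Where more than one anaesthetist is involved, the most senior anaesthetist should be asked to complete the CRF".
- Section 9.2: "Data will be collected onto paper CRFs by either local investigators or the anaesthetic team involved with the case".

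The CRF in Appendix 2 prints one ease scale per technique. It records the grade of the initial airway manager and, if there was one, of the second. Neither the scales nor the CRF notes direct the ease items to the airway manager, and there is no field for the role or grade of the person answering.

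**The concern.** For a subjective rating, the rater is part of the measurement. Section 6.1 promises the view of the person who handled the airway. Section 9.1 allocates the form by seniority, or to an assistant, whether or not that person handled it. If sites follow the completion rule literally, the outcome becomes a mixture of operator and observer scores. Who rated then depends on the operator's grade and on whether a second anaesthetist was involved.

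The exposure data make this more awkward. Section 9.1 records the protective equipment worn by the anaesthetist managing the airway, so a tabulation of ease by equipment could pair one person's equipment with another person's impression. What is at stake is the meaning of one secondary outcome. An analysis plan cannot repair it, because no later analysis can recover a rater who was never recorded.

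**Working it through.** **No figure in the plan bears directly on this point.** The only sample-size figure is the 1822 in Section 10.1 and Appendix 4. The Appendix 4 formula, with N = 1,000,000, p = 0.05, d = 0.01, design effect 1 and Z = 1.96, gives

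n = N·p(1−p) / [(d²/Z²)(N−1) + p(1−p)] = 1821.4, rounded up to 1822.

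The expected recruitment also reproduces: 50 centres × 18 procedures a day × 4 days = 3600. Neither number depends on who gives the ease scores.

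**Applying the completion rules case by case:**

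1. *One anaesthetist, who completes the form.* The rating is the operator's. No conflict.
2. *One anaesthetist, but the assistant completes the form.* Section 9.1 permits this. The rating is the assistant's unless the assistant happens to ask.
3. *Several anaesthetists, and the most senior manages the airway.* The rating is the operator's. No conflict.
4. *A less senior anaesthetist manages the airway and a senior supervises without taking over.* The rule names the senior, who is not the operator. Here the rule itself conflicts with the outcome definition.
5. *A second manager takes over.* The protocol foresees this, including the case where "the supervising anaesthetist requests a second individual to take over management of the airway". A senior who takes over is also an operator, so that person's score is an operator's score. But there is one scale per technique, so the form does not show whether it describes the first manager's attempt or the second's. If the most senior person present was neither manager, the score is again a non-operator's.
6. *A local investigator records the data.* Section 9.2 permits this. The source of the rating is not stated.

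**Can the cases be separated afterwards?** In case 4 the dataset holds the junior's grade as initial manager and a blank for the second, because CRF note 6 reserves that field for someone who took over. A junior working alone and rating their own airway leaves the same entries. Case 2 likewise looks the same as case 1. The form has no field showing that a supervisor was present, or who answered.

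**Scale.** The documents give no share for cases 2, 4, 5 or 6. Purely as an assumption, if a share s of the 3600 expected forms carried a non-operator rating, the count would be 3600 × s:

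- s = 5%: 180 forms
- s = 10%: 360 forms
- s = 25%: 900 forms
- s = 50%: 1800 forms

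The width of this range shows that the size cannot be fixed from the protocol. It is not an estimate.

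**The case against.** The strongest reply is that completing a form is not the same as being the source of every answer. Section 6.1 already says the assessment is the operator's. The same form asks for the number of attempts and the best laryngoscopic view, which a supervisor may also need to get from the person at the airway. Section 9.1 makes local investigators responsible for accurate data and allows them to cross-check other sources. On this reading a senior can simply write down the operator's score. That is possible, but nothing asks for it. A request for a personal impression, put to a named respondent with no other rater mentioned, will naturally be answered with that respondent's own view. The form would not show which happened.

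A second reply is that one accountable senior respondent is a sensible choice for an unfunded service evaluation. That stands for the rest of the form. It does not settle who should give a rating defined as the operator's.

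A third is that the recorded grades offer a partial check: where a consultant was the initial manager and no second manager was needed, a senior-completed form is more likely to be the operator's own. That stands too, but the comparison would be confounded by grade and would not exclude forms completed by an assistant.

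Some stronger readings are tempting, and the documents do not support them:

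- *That many ratings will come from non-operators.* No share is given.
- *That scores for rescued airways will drift towards easy.* A senior who watched a failed attempt could equally score it as difficult.
- *That Aim 2 is compromised.* Section 5 frames that aim in terms of complications, and the regression in Section 10.2 is for the primary outcome. No comparison of ease scores by equipment or grade is specifically planned.
- *That only the initial manager's score before any takeover counts.* The protocol does not define the operator that way, and a second manager who takes over is an operator too.

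**Conclusion.** The point holds as a conflict between an outcome definition and its collection rule. For supervised airways without a takeover, Section 9.1 directs the rating to someone other than the operator. For assistant-completed forms it permits the same. After a takeover it leaves unclear whose attempt is scored. None of these forms can be identified later.

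The conclusion rests on reading the completion rule as written and on the absence of any rater instruction or rater field in Section 9.1, the CRF or its notes. It needs no assumption about how often these cases occur, and their number and any direction of bias remain unknown. The effect is confined to this secondary outcome, which the synopsis does not list among its secondary objectives or endpoints. It is worth correcting because the remedy is small and must be in place when the forms are completed.

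**What to change.** Add to Section 9.1, and as a note on the CRF, that each of the three ease scores is given by the person who managed the airway with that technique, even if the senior anaesthetist or an assistant completes the rest of the form.

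Add one tick for the rater's role: initial airway manager, second airway manager, or other.

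Summarise the secondary outcome on ratings by airway managers and show the other ratings separately.

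The cost is about one sentence and one tick box. In supervised cases two people may have to touch the form, and some ratings will leave the main summary.

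If the sponsor prefers to keep the present completion rule unchanged, the minimum is to rename the outcome as the respondent's assessment and still record the respondent's role.

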Main Inclusion Criteria	Adult patients undergoing general anaesthesia for relevant procedures during the pre-defined study window (as defined by this study, see Section 7) within hospitals affiliated with the Pan-London Perioperative Audit and Research Network (PLAN) and other regional trainee networks
Data collected/storage (if applicable)	Anonymised data will be stored on the PLAN REDCap secure data capture server.

4 Introduction

Although most airway management is uncomplicated, when complications occur they can be catastrophic resulting in significant morbidity and mortality [1]. The severe acute respiratory syndrome coronavirus-2 (SARS-CoV-2) pandemic has resulted in significant changes to airway management [2] due to concern over transmission of aerosolised virus particles to healthcare professionals [3]. Initial reports suggest that patients infected with SARS-CoV-2 may be more at risk of airway complications including hypoxaemia [4], airway trauma [5], and airway oedema [6]. While it is possible SARS-CoV-2 itself may be a risk factor for airway complications, aerosol precautions, designed to reduce the transmission of virus particles to healthcare workers, may also contribute. These aerosol precautions include modified anaesthetic techniques, unfamiliar equipment, and personal protective equipment (PPE).

Anaesthetic management varies, in part, depending on the patient's coronavirus disease 2019 (COVID-19) status. Personal protective equipment for droplet precautions is advised for staff dealing with COVID-19 negative patients and comprises eye protection, gloves, and surgical facemasks at the minimum [7]. COVID-19 positive or COVID-19 unknown patients require staff to use a greater level of aerosol precaution PPE, comprising respirator masks (e.g. FFP3), long-sleeved gowns, gloves and eye protection. It is currently not known whether use of aerosol precaution PPE and other methods used to reduce viral transmission during airway interventions increases the risk of airway complications, but it may be a contributing factor to difficult intubations reported in COVID-19 patients [6, 8].

We aim to describe airway management and the different components of the bundle of aerosol precautions used to protect healthcare workers, and report the associated incidence of airway complications.

5 Trial objectives and purpose

Aims

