- 1. To determine the incidence of airway complications in patients undergoing general anaesthesia during the COVID-19 pandemic.
- 2. To identify components of the aerosol precaution bundle (including PPE and anaesthetic techniques) which may be associated with a greater risk of airway complications.

6 Study design & Flowchart

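### Body protection is recorded without a 'none worn' option, so staff at the protocol's own droplet-precaution minimum cannot be told apart from unanswered items or unlisted PPE.

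*Protocol*

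**What the plan says.** Section 9.1 lists four PPE items for the anaesthetist managing the airway:

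- The first item reads "Eye protection: visor; goggles; other".
- For the mask, the entry is "Respiratory protection: surgical mask; disposable FFP2/3 mask; re-usable FFP2/3 mask; powered air-purifying respirator; other".
- Clothing is covered by "Body protection: plastic apron; long-sleeved gown; hazmat suit; other".
- The fourth item is "Gloves: single pair; double pair; other".

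Each list ends in a residual option, and none has an entry for nothing worn.

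The Introduction (Section 4) describes two levels of PPE. Droplet precautions, advised for COVID-19 negative patients, "comprises eye protection, gloves, and surgical facemasks at the minimum". The aerosol level, for positive or unknown patients, is described as "comprising respirator masks (e.g. FFP3), long-sleeved gowns, gloves and eye protection". The gown appears only in the second set.

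Two parts of the plan rest on these items. Aim 2 in Section 5 is "To identify components of the aerosol precaution bundle (including PPE and anaesthetic techniques) which may be associated with a greater risk of airway complications". A secondary outcome in Section 6.1 reads "Risk of composite outcome of airway complications will be reported for each individual component of the aerosol precaution bundle". Section 10.2 plans univariate odds ratios and univariable and multivariable logistic regression.

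**The concern.** An odds ratio for wearing a gown needs an identifiable group without one. Part of that group wears an apron and can be coded. The rest wear neither, which Section 4 allows at the droplet minimum, and no listed option describes them.

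Such an anaesthetist can do one of two things. Left blank, the field may mean that nothing was worn or that the question was missed. Ticked as the residual option, it puts people wearing nothing together with people wearing something unusual.

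If blanks are later treated as missing, those who wore nothing and left the field blank drop out, and the gown is compared mainly with the apron. If blanks are treated as nothing worn, unanswered forms enter the reference group. An analysis plan can choose between these two errors, but it cannot recover what the form did not capture.

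**Working it through.** **1. The plan's own figures.** Appendix 4 gives n = DEFF·N·p(1−p) / [(d²/Z²)(N−1) + p(1−p)]. With N = 1,000,000, p = 0.05, d = 0.01, Z = 1.96 and DEFF = 1:

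- numerator: 1,000,000 × 0.0475 = 47,500
- denominator: (0.0001/3.8416) × 999,999 + 0.0475 ≈ 26.078
- n ≈ 1821.4, rounded up to 1822, as stated

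Expected recruitment is 50 centres × 18 a day × 4 days = 3600, also as stated. Neither figure uses the PPE items, so neither changes.

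**2. Option lists against Section 4.**

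| Item | In droplet minimum? | In aerosol set? | Codable at droplet minimum? |
|---|---|---|---|
| Eye | yes | yes | yes |
| Respiratory | surgical mask | respirator | yes |
| Gloves | yes | yes | yes |
| Body | no item | long-sleeved gown | no, unless an apron or other garment is worn |

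The gap at the protocol's own minimum is confined to body protection. The other three items lack an answer only for staff below that minimum.

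**3. Is a blank defined anywhere?** CRF notes 1 to 11 in Appendix 2 give no rule for a blank PPE field. Other fields are handled: note 6 covers a blank for the second airway manager, note 8 covers a blank for intubation attempts and laryngoscopy grade, and the ease-of-airway ratings have a category for not attempted. Section 9.1 states a free-text option for adjunct equipment but not for PPE.

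**4. Illustration on assumed values.** The protocol gives neither the frequency of no body protection nor a rate of unanswered items. Suppose a fraction f of 3600 patients is managed with no body protection, all of those forms are left blank, and 5% of the remaining forms are blank by oversight. Then:

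- blanks = 3600f + 0.05 × 3600(1−f)
- share of the sample lost if blanks are dropped = blanks / 3600
- share of the blank group that did wear something = 0.05 × 3600(1−f) / blanks

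| f (assumed) | Blanks | Lost if dropped | Misclassified if read as none |
|---|---|---|---|
| 10% | 360 + 162 = 522 | 14.5% | 31% |
| 30% | 1080 + 126 = 1206 | 33.5% | 10% |
| 50% | 1800 + 90 = 1890 | 52.5% | 5% |
| 70% | 2520 + 54 = 2574 | 71.5% | 2% |

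The two errors move in opposite directions. When few staff wear nothing, reading blanks as none is the riskier choice. When many do, dropping blanks costs more. The table shows this pattern and does not estimate what will happen in the study.

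**The case against.** A reader might infer that the PPE lists are closed and that all four items lose their unexposed group. The protocol does not support this. Every list has a residual option, and staff at the droplet minimum have a valid answer for eyes, mask and gloves. The contrast between surgical mask and respirator can be coded in full.

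A blank body item beside ticked mask and gloves also says something, and a wholly blank PPE block can be recognised. Section 9.1 makes local investigators responsible for completeness, with cross-checking where appropriate, database validation, and paper forms kept for six months. These points stand and will reduce the ambiguity. They do not remove it. A single overlooked item still looks the same as nothing worn, nothing in the protocol says that PPE worn is recorded in patient notes, and the local ID is detached once the form is complete. A required field without a 'none' choice would push these cases into the residual option.

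The text of the CRF in Appendix 2 is broken around the eye and body boxes, so the printed form cannot be fully checked there. Section 9.1 is explicit, and the legible respiratory and glove lists agree with it, but the form or REDCap could differ for eye and body.

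Finally, handling of missing data may properly sit in an analysis plan that is not shown. That is true of the choice of method. It does not reach the information that was never collected.

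**Conclusion.** The point holds for body protection. Section 9.1 offers no answer for staff who meet the droplet minimum of Section 4 without a gown, apron or other garment, and no rule says how to read a blank. The consequence is exposure misclassification or selective loss in one component of Aim 2 and of the per-component secondary outcome. It extends to the other three PPE items only where practice falls below the minimum. The primary incidence estimate and the 1822 figure do not depend on it.

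The size is unknown. A reader might infer from the illustration that a large part of the sample will be lost. That would need three things the protocol does not give: a known frequency of no body protection, every such form left blank rather than ticked under the residual option, and a rule that drops blanks. Droplet precautions are also described as a minimum, so some staff at that level may wear an apron, which can be coded. The protocol names no formal reference group; that staff wearing neither gown nor apron belong in the comparison follows from the aim of relating each component to risk.

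**What to change.** Add a 'None worn' box to body protection in Section 9.1, the CRF and REDCap, and for consistency to eye, respiratory and glove protection. Require an answer to each of the four items, so that a blank means missing and nothing else. The required setting should come only together with the new box.

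The cost is four tick boxes and a database setting, on a one-page form that becomes slightly more crowded. No extra patients or staff are needed.
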